STATEMENT OF COMPLIANCE

The trial will be carried out in accordance with International Conference on Harmonisation Good Clinical Practice (ICH GCP) and the following:

- United States (US) Code of Federal Regulations (CFR) applicable to clinical studies (45 CFR Part 46, 21 CFR Part 50, 21 CFR Part 56, and 21 CFR Part 312)

National Institutes of Health (NIH)-funded investigators and clinical trial site staff who are responsible for the conduct, management, or oversight of NIH-funded clinical trials have completed Human Subjects Protection and ICH GCP Training.

The protocol, informed consent form(s), recruitment materials, and all participant materials will be submitted to the Institutional Review Board (IRB) for review and approval. Approval of both the protocol and the consent form must be obtained before any participant is enrolled. Any amendment to the protocol will require review and approval by the IRB before the changes are implemented to the study. In addition, all changes to the consent form will be IRB-approved; a determination will be made regarding whether a new consent needs to be obtained from participants who provided consent, using a previously approved consent form

Abbreviated Title: NR in psoriasis

Version Date: 07/21/2023

1 PROTOCOL SUMMARY

1.1 SYNOPSIS

Title:	Pilot Study to Evaluate the Effect of Nicotinamide Riboside on Immune Activation in Psoriasis
Study Description:	Psoriasis is a Th17 linked inflammatory disease and we find that the vitaminB3 analogue nicotinamide riboside (NR) blunts Th1 and Th17 activation in ex-vivo naïve and differentiated T cells from control and psoriasis subjects. These findings supported the proposal of the following hypothesis. Supplementation with NR will blunt systemic immune activation in mild/moderate psoriasis.
Objectives:	
 1) Evaluate the effect of NR on Th17 biology 2) Explore the effect of NR on neutrophils, specifically low-density granulocytes 3) Evaluate whether NR modulates keratinocyte activation in skin lesions in psoriatic subjects 4) Evaluate the effect of NR on HDL regulated reverse cholesterol transport and lipid composition
Endpoints:	The primary outcome will be the change in the Th17 cell cytokine IL-17 secretion in response to T-cell differentiation comparing the baseline versus NR or placebo. The comparisons will be performed using paired two-tailed Student t-tests. Significance will be tested at the 0.05 alpha level in this pilot study.
	Exploratory outcomes are:
	
 1) Evaluate the effect of NR on the T cell transcriptome 2) Explore the effect of NR on low-density granulocytes and neutrophils
Study Population:	Up to 40 male and female subjects of all races between the ages of 18-80 years with mild-moderate psoriasis who live locally will be screened.
Phase:	N/A
Description of Sites/Facilities	Enrollment and study visits will take place at the NIH Clinical Center or via telehealth visits .
Enrolling Participants:	Psoriatic Subjects

Abbreviated Title: NR in psoriasis

Version Date: 07/21/2023

Description of Study Nicotinamide Riboside Chloride 500mg or placebo twice daily by mouth for 28 days.

[figure not shown]
Study Duration: 3 years

Participant Duration: 5-23 weeks

Abbreviated Title: NR in psoriasis

Version Date: 07/21/2023

1.2 SCHEMA

Abbreviated Title: NR in psoriasis

Version Date: 07/21/2023

1.3 SCHEDULE OF ACTIVITIES (SOA)

EVALUATION AND ASSESSMENTS	Screening (A)	Baseline Visit*	28 day Visit *	Safety visit (if applicable)
PROTOCOL TIMEPOINT VISITS		1	2	3
		D0	D28	
Window +/- days	-120Days		+/- 7 D	
Assessments & Consents				
Review Inclusion/Exclusion Criteria	X			
Medical History	X			
Physical Examination	X ³	X ³	X ³	X ³
Medication Review	X	X	X	
Vital Signs		X ³	X ³	X ³
Consent to Study	X	X		
Adverse Event Review			X	X
CHEMISTRY LABS				
Female, Pregnancy Test (blood or urine)	X ¹	X ¹	X ¹	
Acute Care Panel	X	X	X	X
Mineral Panel		X	X	X
Hepatic Panel	X	X	X	X
hs-CRP		X	X	X
Uric Acid	X			
Fasting Lipid Panel		X	X	
HEMATOLOGY LABS				
CBC with differential	X	X	X	X
Research Samples				
PBMC's		X	X	
Serum		X	X	
Procedures				
Skin Punch Biopsy (lesion and non-lesion)		X ³	X ³	
PASI (Psoriasis Area and Severity Index)	X			
Study Medication				
Dispense study pills		X		
Compliance (pill count)			X ²	
Return of study pills			X	
A. Labs and assessments may be used for baseline visit if performed within 14 days				
B. Unscheduled safety visit for those patients with clinically significant ongoing adverse events from month 1 visit or reported to site within 7 days from last dose of study drug. All procedures or testing noted above are optional.				
X ¹ = Pregnancy testing for women with childbearing potential				
X ³ = Optional				
X ² = compliance to be greater than or equal to 75%				
*Study visits are defined by the period of time necessary to complete events described in the protocol and may span several days.				

Abbreviated Title: *NR in psoriasis*

Version Date: *07/21/2023*

All study visits may be performed in person at the NIH CC or virtually using NIH approved TeleMedicine software and approved NIH TeleMedicine guidance. In the event the subject is not able to come to the NIH CC the consent may be obtained by phone, vital signs are optional and reported based on subject's own measurements (if possible), physical exam is optional and none of these changes will be considered a protocol deviation. If there are remaining tablets, they will be returned to the research team at first possible opportunity following NIH pharmacy direction.

Abbreviated Title: NR in psoriasis

Version Date: 07/21/2023

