5. STUDY POPULATION

ELIGIBILITY ASSESSMENT AND ENROLLMENT

All protocol eligibility criteria will be met before dispensing study medication to participants or conducting the biopsy for the baseline visit. Patients will sign the consent prior to any screening tests/procedures done as part of this protocol.

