5.2 EXCLUSION CRITERIA

- Severe psoriasis by PASI (Psoriasis Area and Severity Index) score > 12
- Currently being treated with biologic immune modifying agents.
- Currently on treatment for allergies or other inflammatory diseases.
- Currently taking a multivitamin, Vitamin B or tryptophan supplementation and unwilling to stop within 2 weeks of baseline visit..
- Unwillingness/inability to provide informed consent
- ALT > x3 upper limit of normal, hepatic insufficiency or active liver disease
- Recent history of acute gout
- Chronic renal insufficiency with creatinine > 2.5mg/dl
- Pregnant (or attempting to become pregnant) women
- Current participation in another drug study
- History of intolerance to NR precursor compounds, including niacin or nicotinamide
- Study adherence concerns
- Individuals with diabetes type 1 and 2 who use insulin
- Women of child-bearing potential unwilling to use contraception or unwilling to practice abstinence
- Breastfeeding women unwilling to stop breastfeeding
- Immunization administered within 30 days of participation and no plans for immunization while participating in the study

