5.3 INCLUSION OF VULNERABLE PARTICIPANTS

Rationale for the Exclusion of Children

Subjects under 18 years of age will not be considered for inclusion in this protocol because there is no direct benefit from participating in this study and the volumes of blood levels drawn exceed

Abbreviated Title: NR in psoriasis

Version Date: 07/21/2023

minimal risk for children

Rationale for the exclusion of pregnant women

The subject must not be pregnant or actively seeking pregnancy in order to participate in this study. NR has not been determined to be safe in pregnancy or breastfeeding women. A recognized form of contraception must be used by subjects while enrolled. Contraception use will be determined during telephone screening and confirmed at the screening visit.

Rationale for the exclusion of cognitively impaired subjects

Subjects with cognitive impairment will not be considered for inclusion because there is no direct benefit from participating in this study.

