8 STUDY ASSESSMENTS AND PROCEDURES

8.1 SCREENING PROCEDURES

Subjects with mild to moderate psoriasis will be recruited from [name] psoriasis clinic at the NIH or from outside and self- referrals If a subject is recruited from a source outside the NIH then the screening and/or baseline visit #1 will be in person. The remainder of the visits may be via telehealth.

Screening activities performed prior to obtaining informed consent

Minimal risk activities that may be performed before the subject has signed a consent include the following:

- Email, written, in person or telephone communications with prospective subjects
- Review of existing medical records to include H&P, laboratory studies, etc.

Once the research team has identified a potential subject for the study, the subject will be asked to come to the NIH or complete a Telehealth Screening Visit. The study team will consent the subject, allowing time for the subjects to ask questions and make a voluntary decision.

Abbreviated Title: NR in psoriasis

Version Date: 07/21/2023

Once the subject signs the consent, the following tests will be done at the Screening Visit unless any of the tests have been performed under another NIH protocol 2 weeks prior to signing the consent (unless otherwise stated).

Screening Visit (May be combined with Visit 1):

- Basic Metabolic Panel
- Hepatic Panel + uric acid
- CBC + Differential
- Serum pregnancy test for women with childbearing potential (within the past 24 hours)
- History +/- physical exam (physical exam will not be performed at TeleHealth visit)

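### Footnote A of the Schedule of Activities does not exempt the pregnancy test, so a screening test up to 14 days old can stand in for the baseline test when capsules are dispensed

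*Combined protocol and SAP*

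**What the plan says.** **Schedule of Activities (Section 1.3).** The screening column heading carries footnote A: "Labs and assessments may be used for baseline visit if performed within 14 days". The row "Female, Pregnancy Test (blood or urine") sits under Chemistry Labs and is marked at screening, at baseline and at Day 28. Its own footnote, X1, says only which women are tested. Capsules are dispensed at the baseline visit. A further footnote reads: "Study visits are defined by the period of time necessary to complete events described in the protocol and may span several days". Screening may take place up to 120 days before Day 0.

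**Screening procedures (Section 8.1).** The list headed "Screening Visit (May be combined with Visit 1") includes "Serum pregnancy test for women with childbearing potential (within the past 24 hours"). The same section lets screening tests be taken over from another NIH protocol if done in the two weeks before consent, unless the text states otherwise.

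**Eligibility.** Section 5 says: "All protocol eligibility criteria will be met before dispensing study medication to participants". Section 5.2 excludes "Pregnant (or attempting to become pregnant) women". Section 5.3 gives the reason: "NR has not been determined to be safe in pregnancy or breastfeeding women".

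**The concern.** The baseline visit is where exposure starts, so the pregnancy test that matters most is the one that supports dispensing. Footnote A is a general permission over the whole screening column, and read as written it reaches the pregnancy test. Most of the other clinical labs it covers change little in two weeks, but pregnancy status can change in that time.

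The protocol itself appears to treat a two-week-old pregnancy test as too old at screening. Section 8.1 allows two-week reuse of tests from other protocols subject to stated exceptions, and then gives this test a 24-hour limit. Footnote A allows much the same reuse at baseline without that exception.

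At stake is exposure of an early pregnancy to a product whose safety in pregnancy the protocol says is not established. Automatic withdrawal (Section 7.2) and reporting (Section 8.4.8) act only once a pregnancy is known.

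**Working it through.** The plan states no figure for the age of the test at dispensing, so there is nothing to reproduce. The check is to read each rule and count the oldest test that it admits.

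**Inputs**
- Reuse window for screening labs at baseline: 14 days (Section 1.3, footnote A).
- Limit on the screening pregnancy test: 24 hours, or 1 day (Section 8.1).
- Dispensing: baseline visit, Day 0 (Section 1.3). Dispensing is taken to be on Day 0 itself.

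**Oldest pregnancy test at dispensing, by case**

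| Case | Oldest test | Why |
|---|---|---|
| Screening separate, at most 14 days before baseline, result reused | 14 days | Footnote A permits it; no exception |
| Screening separate, at most 14 days before baseline, result not reused | New baseline test | Default in the schedule |
| Screening more than 14 days before baseline | New baseline test | Footnote A no longer applies |
| Screening combined with Visit 1 | About 1 day | The Section 8.1 limit then falls at the dispensing visit |

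Only the first row is a problem. If the baseline visit spans several days, the test could be slightly older than 14 days when capsules are handed over, because the footnote does not say which day of the visit it counts from.

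**Days added by reuse, against a test 1 day before dispensing**
- Reused test 14 days old: 14 − 1 = 13 days.
- Reused test 7 days old: 7 − 1 = 6 days.
- Reused test 3 days old: 3 − 1 = 2 days.

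**Does another rule close the gap?**
- Section 5 makes eligibility a condition of dispensing, but names no test and no test age. A negative result from 13 days earlier could be accepted as meeting it. The schedule marks the criteria review at screening only.
- Footnote X1 gives no timing.
- The 24-hour limit in Section 8.1 belongs to the screening list and does not mention dispensing.

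**Would a new baseline test mean an extra needle stick?** The mineral panel, hs-CRP, fasting lipids, PBMCs and research serum are due at baseline and have no screening sample to reuse. The research draw in Section 8.2.2 is 80 + 20 + 20 = 120 mL, plus 5 to 10 mL for serum, or 125 to 130 mL. Blood is taken anyway, and the schedule also accepts urine.

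**The case against.** The best counter-argument is that the protocol already handles this. The schedule puts a pregnancy test in the same column as dispensing, footnote A is permissive, and Section 5 blocks dispensing to anyone ineligible. Section 8.1 singles out the pregnancy test for a 24-hour limit right after a two-week reuse rule with room for exceptions. A reader could reasonably take that specific limit to override footnote A's general 14 days, which would bring the oldest test down to about one day. In addition, reliable contraception is an inclusion criterion (Section 5.1), and its use is asked about by telephone and confirmed at screening (Section 5.3).

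Much of this stands. It rules out a stronger reading that a reader might infer: that nothing connects pregnancy testing to dispensing. The default baseline test and the eligibility condition both do. Nor do footnote A and Section 8.1 contradict each other; they govern different steps and are not reconciled. The override reading is sensible, but the text does not state it, and staff who followed footnote A literally would not be departing from the schedule.

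It would also be tempting to count the capsules taken before the Day 28 test as the size of the problem. That exposure follows any pregnancy missed at dispensing and is the same after the correction, so it does not measure this point.

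A strict rule of 24 hours before dispensing could also be unworkable. Section 1.3 allows virtual visits and Section 8.2 allows collection at outside laboratories. That objection is sound, and the correction has to allow for it.

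**Conclusion.** The gap is real but narrow. As written, the schedule permits dispensing on a pregnancy test up to 14 days old, at most 13 days older than the protocol's own 24-hour standard. This happens only when screening is a separate visit no more than 14 days before baseline and the site chooses to reuse the result. It rests on reading footnote A literally and on dispensing on Day 0.

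The documents do not give the number of women of childbearing potential or the actual screening-to-baseline intervals, so the number affected cannot be estimated. Required contraception lowers the risk, and even a test within 24 hours can miss a very early pregnancy, so the correction shortens the untested interval without removing it. Power, sample size, alpha and the primary analysis are untouched. This is a minor participant-safety correction, worth making because it is so cheap.

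**What to change.** Change two footnotes in Section 1.3:

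1. **Footnote A:** after the opening mention of labs and assessments, insert *except the pregnancy test*.
2. **Footnote X1:** add *a negative baseline result (blood or urine) is required before capsules are dispensed, within 24 hours where feasible, or before the first dose if the visit is remote*.

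Naming blood or urine in X1 also makes clear that the serum requirement in Section 8.1 applies to the screening test and that urine is acceptable at baseline, as the schedule row already allows.

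The cost is at most one pregnancy test per affected woman, and that test is already scheduled. It can use the baseline blood draw, or urine if that draw falls more than 24 hours before dispensing. For remote visits, the site must obtain the result before the first dose.

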2 INTRODUCTION

2.1 STUDY RATIONALE

Over the past two decades, inflammation has been identified as an important pathogenic process in cardiometabolic diseases (CMD) such as atherosclerotic cardiovascular disease (CVD), dyslipidemia, insulin resistance, diabetes and obesity. Over the last eight years, the [name] laboratory within the NHLBI DIR has studied psoriasis, a common, chronic inflammatory T-cell skin disease associated with increased CVD and CMD as a model to understand the effect of chronic inflammation on these disease states. At the same time, the degree of obesity has been linked to the severity of psoriasis and caloric restriction ameliorates dermatologic manifestations of this disease. The [name] laboratory is studying the effects of caloric restriction on immune activation and is demonstrating the caloric-restriction mimetic vitamin B3 analogue nicotinamide riboside (NR) blunts both adaptive and innate immunity. Furthermore, the in-vitro administration of NR to CD4⁺ T cells extracted from psoriatic subjects blunts IL-17 production. Given this, these two laboratories will collaborate in a pilot study to evaluate whether the administration of a nutritional supplement NR has anti-inflammatory effects in a small cohort of subjects that have untreated mild to moderate psoriasis.

2.2 BACKGROUND

Psoriasis is a chronic inflammatory skin disease that affects 2–3% of the US population. In addition to its skin and joint manifestations, psoriasis predisposes to premature cardiovascular co-morbidities in part through immune activation and systemic inflammation-induced atherosclerosis.^{1, 2} The skin-initiated immune activation through non-professional immune cells including keratinocytes and fibroblasts, initiates and amplifies innate and adaptive immune activity of monocytes/macrophages, neutrophils and their subsets (low-density granulocytes), and effector T-cells (predominantly Th1 and Th17 subsets) which concurrently exacerbate local disease and initiate systemic sterile inflammation. The centrality of immune activation in psoriasis is reinforced by the therapeutic efficacy of anti-TNF α and anti-IL-17 therapy.³⁻⁵

The contribution of caloric-load to psoriasis has been long debated, however, epidemiology and meta-analysis data support that the incidence of obesity is higher in psoriasis and that the greater the severity of psoriasis, the higher the incidence of obesity.⁶⁻⁸ The role of caloric excess in the pathophysiology of psoriasis is further strengthened by the effects of limiting calories on disease activity.⁹⁻¹¹ Taken together, these data support that nutrient levels may play a role in the pathophysiology of psoriasis and at the same time employing strategies to mimic caloric restriction/fasting may contribute to disease-amelioration.

The [name] laboratory employs fasting as a model system to investigate immune cell function and have identified biological pathways that explain how fasting blunts immune activation in monocytes/macrophages and CD4⁺ T cells in both healthy subjects and in those with a mild inflammatory disease (steroid-naïve asthma subjects). More recently we have begun to explore the role of a caloric restriction/fasting *mimetic*, nicotinamide riboside (NR – a vitamin B₃ analogue and precursor for NAD⁺ biosynthesis) on immune modulation. Our initial clinic study using 1000 mg of NR daily blunted immune pathways important in CVD both in monocytes and CD4⁺ T cells, however, we did not investigate the effects of NR on neutrophils.

Abbreviated Title: NR in psoriasis

[figure not shown]
Version Date: 07/21/2023

Given that these cell types contribute to the pathophysiology of psoriasis and that disease activity may be ameliorated by dietary restriction, we reasoned that NR may blunt psoriasis-linked immune activation pathways. To explore this, a collaboration was established with the [name] laboratory and the *in-vitro* effects of NR were tested on CD4⁺ T cells extracted from biologic treatment-naïve psoriatic subjects. NR was found to blunt the secretion of IFN γ and IL-17, predominantly Th1 and Th17 cytokines respectively. Because these cytokines are instrumental in the progression of the dermatologic, systemic and vascular consequences in psoriasis, we propose a pilot interventional study to explore the immunological consequences of NR supplementation in biologic naïve, mild to moderate psoriatic subjects.

Preliminary Data:

To study the effect of NR on T cell function, blood was drawn from psoriatic subjects enrolled on protocol 13-H-0065 and from matched normal control subjects enrolled on protocol 16-H-0126. Psoriatic subjects were biological anti-immune therapy naïve. Primary peripheral bloodmononuclear cells (PBMCs) were isolated by density centrifugation. CD4⁺ T cells were then negatively selected from PBMCs and cell purity was confirmed at > 95%.

[figure not shown]
CD4⁺ T cells were activated in culture on plates coated with α CD3 and α CD28 antibodies for 3 days in the presence or absence of 0.5mM NR. Alternatively they were differentiated into two T cell subtypes by incubation with the specific polarization media (\pm NR) - Th1 (20 ng/ml IL-12 and 10 μ g/ml α IL-4) and Th17 (20 ng/ml IL-6, 2 ng/ml TGF- β 1, 10 ng/ml IL-1 β , 10 ng/ml IL-23, 10 μ g/ml α IL-4, and 10 μ g/ml α IFN γ). Supernatants were collected, centrifuged to remove cells and debris, and stored at -80°C. The levels of cytokines, including IL-1 β , IFN γ , IL-4, IL-5, IL-13, IL-17, IL-22, IL-9, IL-2, and MIP-1 β were measured by ELISA (R&D Systems). Results were normalized to cell number using the CyQuant cell proliferation and BCA protein assays.

[figure not shown]
Abbreviated Title: NR in psoriasis

Version Date: 07/21/2023

C

D

Abbreviated Title: NR in psoriasis

Version Date: 07/21/2023

Figure Legend: **A, B.** IFN γ and IL-17 release in activated CD4 $^{+}$ T cells isolated from Psoriatic subjects (PS) and control subjects (PSC). CD4 $^{+}$ T cells was activated with 0.5 mM NR and 10% autologous serum for 3 days by α CD3 and α CD28 (n=7). **C, D.** IFN γ and IL-17 release in differentiated CD4 $^{+}$ T cells isolated from Psoriatic subjects (PS) and control subjects (PSC). CD4 $^{+}$ T cells was differentiated with 0.5 mM NR and specific differentiation media with autologous serum for 3 days by α CD3 and α CD28 (n=6). Th1 differentiation supplement (Stemcell Technologies), Th17 differentiation supplement (R&D). PS age (y), 54.43 \pm 14.41 (range: 32-72); PS gender, 1 female and 6 males. Healthy volunteers (PSC) were paired with the psoriatic subjects for age (\pm 5 years) and sex. P value * $<$ 0.05 and ** $<$ 0.01.

These data show that NR blunts Th1 and Th17 activation in naïve and differentiated T cells and that the psoriatic subjects exhibited elevated IL-17 responsiveness, which is a consistent signature of this disease. These findings supported the proposal of the following hypothesis.

